# 6.4.3 Clinical Laboratory Assessments

The following laboratory variables will be determined as outlined in Table 4 below:

Table 4 Clinical Laboratory Assessments

Test	Parameters				
Hematology	CBC	Leukocytes (WBC)			
	Hb1Ac	Differential WBC			
	Hemoglobin	Platelets			
	Hematocrit				
	Erythrocytes (RBC)	Erythrocytes (RBC)			
Biochemistry	Sodium	GGT			
	Potassium	CPK			
	Magnesium	Total bilirubin			
	FSH (post-menopausal females only) a	Total protein			
	Calcium	Albumin			
	Chloride	Total Cholesterol			
	Glucose	Low-density lipoprotein			
	Creatinine	High-density lipoprotein			
	ALP	Triglycerides			
	AST	TSH, fT3 and fT4 a			
	ALT				

Coagulation	INR PT	aPTT
Serology	HBsAg a HCV a	HIV type 1 or type 2 a
Urinalysis	pH glucose ketones specific gravity HCG (females of child-bearing potential only)	nitrite protein bilirubin blood

AST = aminotransferase; ALP = alkaline phosphatase; ALT = alanine transaminase; CBC = complete blood count; CPK = creatine phosphokinase; FSH = follicle-stimulating hormone; GGT = gamma-glutamyl transferase; Hb1Ac = glycated hemoglobin; HBsAg = hepatitis B surface antigen; HCG = human chorionic gonadotropin; HIV = human immunodeficiency virus; INR = international normalized ratio; PT = prothrombin time; aPTT = activated partial thromboplastin time; RBC = red blood cells; fT3 = free tri-iodothyronine; fT4 = free thyroxine; TSH = thyroid-stimulating hormone; WBC = white blood cells.

Any value outside the normal range will be flagged for clinical interpretation by the investigator or designee at the site. In this study, ALT or AST > 2 times the upper limit of normal, or Child-Pugh class B and C (i.e., including total bilirubin, albumin, and INR values), will be exclusionary. For transaminase liver enzymes, a repeat laboratory assessment may be performed if outside of the normal range. If the transaminases remain elevated the investigator should consider stopping study medication and withdrawing the subject as described in Section 5.8.

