A medical alert for potential Hy's laws cases (possible drug-induced liver injury) will be issued based on laboratory values and supported by Medical Monitor interpretation. Investigators, the Sponsor, Medical Monitor, and MMS (the Sponsor's designated vendor for Drug Safety and Pharmacovigilance) will immediately be notified when the above criteria have been met through a central laboratory alert. The AE eCRF should be completed within 3 business days. Every effort to determine the cause of the liver enzyme abnormalities must be made, and close monitoring should be initiated in conjunction with the Medical Monitor and in accordance with the FDA Guidance for Industry, Drug-Induced Liver Injury: Premarketing Clinical Evaluation, July 2009.

Criteria for potential Hy's law cases are as follows:

- ALT or AST  $\geq$  3 × ULN AND
- Total bilirubin  $\geq 2 \times ULN \text{ AND}$
- Alkaline phosphatase < 2 × ULN

Typically, all 3 analytes will be obtained from the same sample, but they may come from multiple samples taken within a 24-hour period. This requirement applies from the time the subject signs the ICF for the study until 4 weeks after the final protocol-defined study visit or the last known dose of study treatment (if the final visit does not occur).

<sup>a Measured only at Screening for eligibility; not included in subsequent safety labs.

Any clinically significant abnormalities from Screening labs must be discussed with the Medical Monitor to confirm eligibility of the subject. Additional testing during the study may be done if medically indicated. If a clinically significant abnormality is found in the samples taken after dosing, during the study, and/or at the safety follow-up visit, it should be recorded as an AE and the subject will be followed until the test(s) has (have) normalized or stabilized.

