- Alkaline phosphatase < 2 × ULN

For the Elevated Liver Tests summary, the list of lab test with criteria will be considered.

Confidential Page 25 of 57

- i) Alanine Aminotransferase (Normal <=ULN, >1 3 x ULN, >3 5 x ULN, >5 10 x ULN, >10 20 x ULN, >20 x ULN)
- ii) Aspartate Aminotransferase (Normal <=ULN, >1 3 x ULN, >3 5 x ULN, >5 10 x ULN, >10 20 x ULN, >20 x ULN)
- iii) Alkaline Phosphatase (Normal <=ULN, >1 2 x ULN, >2 x ULN)
- iv) Bilirubin (Normal <= 2 x ULN, >2 x ULN)
- v) Hy's Law: ALT/AST>=3xULN and BILI>=2xULN (Criteria Not Met, With ALP <2 x ULN, With ALP >=2 x ULN)
- vi) Alkaline Phosphatase >=2 x ULN (Criteria Not Met, With ALT/AST <2X ULN, With ALT/AST >=2X ULN)

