#### 9.6 Visit Windows / Unscheduled Visits

Visit windowing will be applied for the analyses which use visit categories. For categorical visit summaries, all visits including early termination assessments and unscheduled visits will be included with the closest scheduled post-baseline visit that includes the efficacy or safety assessment, based on number of days since Day 1. For the primary variable of ERP P300 latency effect, if multiple assessments fall within the same analysis window, pre- and post-dose measurement will be averaged within the analysis window for this variable. For all other efficacy assessments, if multiple efficacy assessments fall within the same analysis window (other than baseline), any non-missing efficacy assessments will be averaged. For all non-efficacy assessments, a last-within-window approach will be used.

The analysis windows for ERP P300, ADAS-Cog13 and COWAT are:

	Protocol-Specified	Analysis-Specified
Analysis Visit	Day	Interval
Week 2	Day 14	Day 2-63
Week 12	Day 84	Day 64-112
Week 20	Day 140	Day 113-161
Week 26	Day 182	Day 162-196
Week 30	Day 210	Day 197-218

The analysis windows for C-SSRS, Physical and Neurological Exams, EG, Vital Signs, Labs are:

	Protocol-Specified	
Analysis Visit	Day	Analysis-Specified Interval
Week 2	Day 14	Day 2-28
Week 6	Day 42	Day 29-63
Week 12	Day 84	Day 64-98
Week 16	Day 112	Day 99-126
Week 20	Day 140	Day 127-161
Week 26	Day 182	Day 162-196
Week 30	Day 210	Day 197-218

The analysis windows for GDS are:

Confidential Page 32 of 57

	Protocol-Specified	
Analysis Visit	Day	Analysis-Specified Interval
Week 12	Day 84	Day 2-133
Week 26	Day 182	Day 134-196
Week 30	Day 210	Day 197-218

The analysis visit windows for MMSE is:

Analysis Visit	Protocol-Specified Day	Analysis-Specified Interval
Week 12	Day 84	Day 2-112
Week 20	Day 140	Day 113-161
Week 26	Day 182	Day 162-218

The analysis windows for MDS-UPDRS, NMSS, ADCS-ADL23, ADCS-CGIC, ADCS-CaGIC, ADCS-CGIS, and PK are:

Analysis Visit	Protocol-Specified Day	Analysis-Specified Interval
Week 12	Day 84	Day 2-133
Week 26	Day 182	Day 134-218

Confidential Page 33 of 57

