### 10.6.6 Columbia-Suicide Severity Rating Scale

Count and percentage of C-SSRS responses will be generated over the visit. This summary will also be produced for each disease type and AChEI usage within disease type.

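### The last-within-window rule in SAP 9.6 lets an early-termination or repeat record replace an earlier abnormal lab value or positive C-SSRS form in by-visit tables, and no worst-value or any-time rule restores it

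*SAP*

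**What the plan says.** SAP 9.6 sets the scope first: "Visit windowing will be applied for the analyses which use visit categories". Within that scope, "all visits including early termination assessments and unscheduled visits will be included with the closest scheduled post-baseline visit", and then, for every non-efficacy assessment, "a last-within-window approach will be used". One set of windows serves the C-SSRS, examinations, ECG, vital signs and laboratory data.

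Three other parts of the SAP depend on how that rule is read:

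- **Laboratory tables (10.6.2).** Observed values and changes are summarised by analyte and visit, including the maximum.
- **C-SSRS (10.6.6).** "Count and percentage of C-SSRS responses will be generated over the visit". The section names no summary over the whole post-baseline period.
- **Liver summary (6.4.3).** "For the Elevated Liver Tests summary, the list of lab test with criteria will be considered". Bands in multiples of ULN and a Hy's law row follow. Nothing says whether the summary uses the last, by-visit or worst value.

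The protocol supplies the extra records. Section 6.4.3 says: "For transaminase liver enzymes, a repeat laboratory assessment may be performed if outside of the normal range". Section 7.4.2 asks subjects who discontinue early to return for an ET visit, and the ET footnote to Table 1 has safety assessments repeated there however recent the previous ones were. Post-screening C-SSRS forms use the Since Last Visit version (Table 1 footnote e).

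**The concern.** The extra records are not a random sample. A transaminase repeat follows an out-of-range value, and an ET visit follows a decision to stop. Where the later record is closer to normal, the by-visit table shows that value and drops the one that led to the repeat or the stop. Because each Since Last Visit C-SSRS form covers its own interval, a later negative form does not carry an earlier positive one forward.

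Safety is a primary objective, and Protocol 1.3 names hepatotoxicity as a potential risk to be closely monitored. SAP section 6 makes efficacy exploratory after early stopping but keeps the safety summaries as planned, so these tables are the main surviving output. Protocol 8.4.2 also planned frequencies of high and low values and shift tables. The visible text of SAP 10.6.2 does not carry these over, which puts more weight on a liver summary whose selection rule is undefined.

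**Working it through.** **Inputs.** Nominal days and windows come from SAP 9.6. The ±7-day visit allowance comes from SAP Appendix 2 (Protocol Table 1).

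**Reproducing the windows.** Each upper bound should be the midpoint of adjacent nominal days: (14+42)/2 = 28, (42+84)/2 = 63, (84+112)/2 = 98, (112+140)/2 = 126, (140+182)/2 = 161, (182+210)/2 = 196. The last bound, Day 218, is taken as stated. All seven windows match the SAP.

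| Visit | Nominal day | Window | Width (days) | Days left after nominal | On-time range (±7) |
|---|---|---|---|---|---|
| Week 2 | 14 | 2–28 | 27 | 14 | 7–21 |
| Week 6 | 42 | 29–63 | 35 | 21 | 35–49 |
| Week 12 | 84 | 64–98 | 35 | 14 | 77–91 |
| Week 16 | 112 | 99–126 | 28 | 14 | 105–119 |
| Week 20 | 140 | 127–161 | 35 | 21 | 133–147 |
| Week 26 | 182 | 162–196 | 35 | 14 | 175–189 |
| Week 30 | 210 | 197–218 | 22 | 8 | 203–217 |

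Every on-time scheduled visit falls inside its own window, so two on-time scheduled records never collide. Only an ET or extra record can displace one.

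**When a later record overwrites.** Take a scheduled visit k days from nominal (k = −7 to 7) and a repeat r days after it. Both fall in the same window if k + r ≤ days left after nominal. There are 7 visits × 15 days = 105 combinations, weighted equally.

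- r = 7: 15×6 + 9 = 99; 99/105 = 94%
- r = 14: 8+15+8+8+15+8+2 = 64; 64/105 = 61%
- r = 21: 1+8+1+1+8+1+0 = 20; 20/105 = 19%
- r = 28: 0+1+0+0+1+0+0 = 2; 2/105 = 2%

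Without the Week 30 window, the counts are 90/90 (100%), 62/90 (69%), 20/90 (22%) and 2/90 (2%).

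**By-visit laboratory example (values assumed).** ALT is 9 × ULN on Day 84 and 1.5 × ULN at an ET visit on Day 95. Both days lie in the Week 12 window, Day 64–98. The Week 12 row uses 1.5 × ULN, and the 9 × ULN value cannot appear in that row's mean or maximum.

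**C-SSRS.** If a positive form on Day 84 is followed by a negative ET form on Day 95, the Week 12 count uses the negative one. No other C-SSRS table in the SAP restores the positive.

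**Hy's law, texts side by side.** On its alert criteria, Protocol 6.4.3 says: "Typically, all 3 analytes will be obtained from the same sample, but they may come from multiple samples taken within a 24-hour period". SAP 6.4.3 repeats the thresholds without that pairing. Suppose Day 84 gives ALT 6 ×, bilirubin 2.5 × and ALP 1.2 × ULN, and an ALT/AST-only repeat on Day 91 gives ALT 2.5 × ULN with AST below 3 × ULN (all assumed). A summary built on last-in-window values would combine the Day 91 ALT with the Day 84 bilirubin and classify the subject as not meeting the criteria. A summary built on same-sample values would count the subject. The SAP does not say which it will be.

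**The case against.** The strongest reply is that SAP 9.6 covers only analyses that use visit categories, and the Elevated Liver Tests summary states no visit dimension. Its Hy's law row reads like a classification of subjects. A reader might infer that the SAP removes liver cases from that summary. The documents do not support this; they leave the rule unstated. The table shells are not visible either, so a worst-value rule there cannot be excluded. This part stands.

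The records also survive elsewhere. SAP 9.1 keeps unscheduled visits in listings, and clinically significant post-dose laboratory abnormalities are recorded as adverse events (Protocol 6.4.3), which are not reduced to a last value. A subject with ALT at 9 × ULN meets a criterion in Protocol 5.8 and would be expected in the discontinuation tables. This stands too, but it is not a full substitute. Adverse event entry depends on the investigator's judgment, those tables show preferred terms and not multiples of ULN, and listings give no incidence.

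Nor is the direction fixed. The transaminase repeat is optional, a rising ALT would be kept at its higher value, and a repeat at 21 days or more mostly falls in another window. Nothing prompts a repeat C-SSRS: Protocol 6.4.8 asks only for contact with the Medical Monitor when the investigator is concerned. A reader might infer a systematic shift towards normal in both measures, but the documents show only that it can happen.

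**Conclusion.** The point holds for by-visit tables. A stated rule can drop an earlier abnormal laboratory value or positive C-SSRS form when an ET or extra record falls in the same window. That is the usual outcome for a repeat one to two weeks later (94% and 61% of visit-day combinations) and uncommon at three weeks (19%). These fractions assume equal weight for each day in the ±7-day allowance. They describe the windows and do not predict how often subjects are affected.

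For the Elevated Liver Tests/Hy's law summary, the finding is only that the selection rule is missing. The number of subjects affected cannot be computed, because the documents give no rates of abnormal values or repeat tests. A reader might turn one lost case into 1/25 = 4 percentage points of an arm. That needs the liver summary to use windowed values, which is not stated, and 25 per arm was the planned size of a trial that stopped early. Severity is should-fix: the tables could mislead on a primary objective, but the data are retained and the remedy is cheap.

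**What to change.** Amend SAP 9.6, 6.4.3 and 10.6.6 before the tables are produced, so that the rule is not chosen after seeing the data:

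1. Limit last-within-window to by-visit descriptive tables of continuous safety variables.
2. State that the Elevated Liver Tests/Hy's law summary uses each subject's worst post-baseline value from all scheduled, unscheduled and ET records. Evaluate Hy's law on analytes from the same sample or within 24 hours, as in Protocol 6.4.3.
3. For the C-SSRS, count a window as positive if any form in it is positive, and add a summary of ideation and behavior at any time post-baseline.

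By-visit laboratory tables would still show the last value, but the liver summary would then hold the peak. Using the scheduled record in those tables instead is optional.

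The cost is SAP wording and minor programming, with no new data and no effect on sample size, alpha or power. The safety tables may look slightly less favourable.

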#### 10 STATISTICAL ANALYSIS METHODS

## **10.1** Subject Disposition

A summary table will be provided for all patients to display the number of subjects randomized, Safety Population, mITT Population, Per Protocol population, and patients who completed or discontinued the study with reason of study discontinuation, by treatment and overall. This summary will be produced for each disease type and AChEI usage within disease type.

Listings will present all information on the End of Study eCRF page and the Protocol Deviations. Another supportive listing will display patients excluded from any analysis population along with the reason(s) for exclusion.

Screen failure data will be listed by reason subjects were found to not be eligible for the study.

Randomization data will also be listed by subject, country, site, randomization number and randomization date.

# **10.2** Demographics and Baseline Characteristics

A summary table will be provided for demographic and baseline characteristics for safety population, presented by treatment and overall. This summary will be produced for each disease type and AChEI usage within disease type.

Variables to be summarized in this table are:

- Gender (male/female)
- Race (white, black or African American, American Indian or Alaska native, Native Hawaiian or other Pacific Islander, Asian, Other)
- Years of Education (years)
- Ethnicity (Hispanic or Latino, Not Hispanic or Latino, Not Reported, Unknown)
- Age (years)
- Age group (<=55, 56-60, 61-65, 66-70, 71-75, 76-80, 81-85)
- Disease Type (Dementia with Lewy bodies, Parkinson's Disease Dementia)
- Baseline MMSE total score
- Baseline MMSE group (Mild (MMSE>=20), Moderate (MMSE<20)),
- Baseline GBA Genotype
- Baseline Weight (kg)
- Baseline Height (cm)
- Baseline Body mass index (BMI, kg/m^2)
- AChEI usage (Yes, No)

Listings will present all data on the demographics, baseline characteristics, clinical diagnosis, medical history CRF pages for safety population.

Confidential Page 34 of 57

#### 10.3 Prior and Concomitant Medications and Procedures

Medications received prior to the date of first dose of double-blind study medication are considered as prior medications. Medications will be considered as concomitant if the start date of the medication is on or after the date of first intake of investigational product or if the start date is prior to the first date of investigational product but the medication is ongoing during the treatment period in the study.

Concomitant medications will be coded using the World Health Organization (WHO) dictionary and will be summarized by generic name and Anatomical Therapeutic Chemical (ATC) classification system level 3 for safety population, by treatment group and overall. This summary will be produced for each disease type and AChEI usage within disease type.

A listing will be generated for prior and concomitant medications. A separate listing will be generated for surgical procedures.

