- 20. Hepatic impairment with alanine aminotransferase (ALT) or aspartate aminotransferase (AST) > 2 times the upper limit of normal, or Child-Pugh class B and C.

Version 3.00 Page 38 of 86 05-NOV-2021

- 21. Malignant tumor within 3 years before Screening, except for the following conditions that are stable in the judgment of the investigator:
  - a) Adequately treated squamous and basal cell carcinoma, or squamous and basal cell carcinoma in situ
  - b) Prostate carcinoma in situ
  - c) Fully-excised (biopsy-proven) melanoma in-situ; Medical Monitor prior approval is required.
- 22. Clinically significant (in the judgment of the investigator) unintentional weight loss within 12 months of Screening.
- 23. The consumption of grapefruit or grapefruit-containing products is prohibited beginning 7 days prior to the first dose of study medication (Day 1) and during the study.
- 24. Food supplements and nutraceuticals with potential effects on cognition, such as Axona and medium chain triglyceride (MCT), are prohibited beginning 7 days prior to the first dose of study medication (Day 1) and for the duration of the study.
- 25. Tetrahydrocannabinol (THC) is prohibited beginning 4 weeks prior to the first dose of study medication (Day 1) and for the duration of the study. Cannabidiol (CBD) without THC is allowed but not on the clinical visit days, except for topical applications.
- 26. Prohibited prior and concomitant medications are excluded within 4 weeks prior to Screening. All allowed medications should remain stable in terms of dose and regimen throughout the study; for medications affecting cognition, the doses should be stable for at least 4 weeks before Screening and throughout the study, unless otherwise noted. If the permissibility of a specific medication is in question, please contact the Medical Monitor prior to randomization (refer to Appendix 1: List of Prohibited Medications; note: this is not an exhaustive list):
  - a) Selegiline and trihexyphenidyl in any form or dosage.
  - b) Memantine in any form, combination, or dosage.
  - c) Donepezil at 23 mg.
  - d) Antipsychotics: low doses (in the judgment of the investigator) are allowed if the subject has received a stable dose before Screening. If these medications are taken on a PRN basis they should not be taken the morning before any cognitive testing.
  - e) Tryptophan supplements.

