# 5.2 Secondary Objectives

- To evaluate the clinical efficacy of ATH-1017 separately on:
  - 1) Cognition and
  - 2) ERP P300 latency

Confidential Page 10 of 57

[figure not shown]
Table 1. Study Objectives and Associated Endpoints

Primary Objectives	Primary Endpoints	
To evaluate the clinical effects of ATH-1017 in subjects with PDD or DLB	The Global Statistical Test (GST) score (O'Brien, 1984) that combines the standardized change from baseline scores at Week 26 for cognition (Alzheimer's Disease Assessment Scale-Cognitive Subscale 13-item version [ADAS-Cog 13 ]) and ERP P300 latency, comparing ATH-1017 to placebo	
To determine the safety and tolerability of ATH-1017 in subjects with PDD or DLB	Analysis of adverse events (AEs), including injection site AEs; changes from baseline for the following variables: vital signs, 12-lead electrocardiogram (ECG), and laboratory tests (chemistry, hematology, urinalysis); concomitant medication assessments, physical and neurological exams, Columbia-Suicide Severity Rating Scale (C-SSRS), and Geriatric Depression Scale (GDS)	
Secondary Objectives	Secondary Endpoints	
To evaluate the clinical effects of ATH-1017 separately on: (1) cognition and (2) ERP P300 latency	
 
ADAS-Cog13 score: change from baseline at Weeks 2, 12, 20, and 26 compared to placebo
 
ERP P300 latency: change from baseline at Weeks 2, 12, and 26 compared to placebo
 
	

Confidential Page 11 of 57

Exploratory Objectives	Exploratory Endpoints

Confidential Page 12 of 57

Confidential Page 13 of 57

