# 9.3 Handling of Partial Dates

If partial dates are recorded for adverse event and concomitant medications, then partially dates will be filled as per Appendix 3. No imputation will be done for other partial dates.

Confidential Page 31 of 57

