# **Appendix 3.** Imputation of Partial Dates

**Table 4.** Imputation Rules for Partial Dates – Adverse Events

Parameter	Missing	Additional Condition	Imputation	
Start Date	D only	M and Y are prior to first study drug dose	First day of indicated month	
		M and Y is same as first study drug dose	Date of first study drug dose	
		M and Y are after first study drug dose	First day of indicated month	
	M and D	Y is prior to first study drug dose	01 Jan of indicated year	
		Y is same as first study drug dose	Date of first study drug dose	
		Y is after first study drug dose	01 Jan of indicated year	
	M, D, and Y	-	assumed to be TEAE	
End Date	D only	M and Y are prior to last study drug dose	Last day of indicated month	
		M and Y is same as last study drug dose	Date of last observation	
		M and Y are after last study drug dose	First day of indicated month	
	M and D	Y is prior to last study drug dose	31 Dec of indicated year	
		Y is same as last study drug dose	Date of last observation	
		Y is after last study drug dose	01 Jan of indicated year	
	M, D, and Y	-	TEAE is ongoing	
	-	Estimated end date is before a complete or imputed AE start date	Last day of the month of AE start date	

D = day; M = month; Y= year; TEAE = treatment-emergent adverse event

Note: The imputation of end date must be later than start date

**Table 5.** Imputation Rules for Partial Dates – Prior and Concomitant Medications

Parameter	Missing	Additional Condition	Imputation
Start Date	D only	M and Y same as M and Y of first study drug dosing	Date of first study drug dose
		M and/or Y not the same as M and Y of first study drug dosing	First day of indicated month
	M and D	Y same as Y of first study drug dosing	Date of first study drug dose
		Y not the same as Y of first study drug dosing	01 Jan of indicated year
	M, D, and Y	none - date completely missing	Date of first study drug dose
End Date	D only	M and Y same as M and Y of last study drug dosing	Date of last study drug dose
		M and/or Y not the same as M and Y of last study drug dosing	Last day of indicated month
	M and D	Y same as Y of last study drug dosing	Date of last study drug dose
		Y not the same as Y of last study drug dosing	31 Dec of indicated year
	M, D, and Y	none - date completely missing	Date of last study drug dose

D = day; M = month; Y = year

Confidential Page 51 of 57

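### SAP Appendix 3 can impute a start date later than the recorded end date, so some medications and adverse events that ended before dosing are counted as concomitant or treatment-emergent

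*SAP*

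**What the plan says.** SAP 9.3 sends incomplete dates to the appendix: "If partial dates are recorded for adverse event and concomitant medications, then partially dates will be filled as per Appendix 3".

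**Medications.** SAP 10.3 has three rules.
- Prior: "Medications received prior to the date of first dose of double-blind study medication are considered as prior medications".
- Concomitant, first limb: "concomitant if the start date of the medication is on or after the date of first intake of investigational product".
- Concomitant, second limb: "if the start date is prior to the first date of investigational product but the medication is ongoing during the treatment period in the study".

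Appendix 3, Table 5 moves the start to the first-dose date in three situations: the date is wholly missing; month and day are missing and "Y same as Y of first study drug dosing"; or only the day is missing and month and year match those of first dosing. No row refers to the end date, and Table 5 has no check that start precedes end.

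**Adverse events.** Table 4 has the same month and year rules for start dates, and presumes an event with a wholly missing start to be treatment-emergent. It has one order check, triggered when "Estimated end date is before a complete or imputed AE start date". The remedy is to move the end to the last day of the month in which the event started. A note beneath the table likewise constrains only the imputed end date. SAP 10.6.1 defines a TEAE as an event beginning or worsening on or after the first-dose date. Protocol 6.4.1.2 says that events between consent and dosing are recorded as pre-treatment.

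**The concern.** Placing an unclear start on Day 1 is ordinary conservative practice when the item might have overlapped treatment. It is not conservative when the record already shows that the item was over. The imputation then overrides recorded data and creates a record that starts after it ends. Two items with the same recorded stop can fall in different categories only because one has a vaguer start.

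Drugs stopped before dosing are expected here: Protocol 4.3, criterion 26 states that "Prohibited prior and concomitant medications are excluded within 4 weeks prior to Screening". Adverse events are collected from consent, so events that resolved before Day 1 are also expected. The outputs at stake belong to the primary safety endpoint, which SAP Table 1 says includes "concomitant medication assessments, physical and neurological exams" as well as adverse events. SAP section 6 keeps the safety summaries as originally intended after early stopping, while efficacy becomes exploratory.

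**Working it through.** The plan gives no figure to reproduce. The check applies the stated rules to test records. The dates are assumptions: first dose 20 Mar 2022, last dose 17 Sep 2022 (Day 182), Week 30 visit 15 Oct 2022.

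**Medications (Table 5, then SAP 10.3)**

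| Case | Recorded start | Recorded end | Date imputed | Concomitant? |
|---|---|---|---|---|
| A | 1 Jun 2021 | 10 Jan 2022 | none | No |
| B | missing | 10 Jan 2022 | start 20 Mar 2022 | Yes |
| C | 2022 only | 10 Feb 2022 | start 20 Mar 2022 | Yes |
| D | Mar 2022 | 12 Mar 2022 | start 20 Mar 2022 | Yes |
| E | 1 Jun 2021 | 2022 only | end 17 Sep 2022 | Yes |
| F | 1 Jun 2021 | Mar 2022 | end 31 Mar 2022 | Yes |
| G | 26 Sep 2022 | 6 Oct 2022 | none | Yes |
| H | 2021 only | 10 Feb 2022 | start 1 Jan 2021 | No |

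- B, C and D show the defect. The imputed start falls after the recorded end by 69 days (21 + 28 + 20), 38 days (18 + 20) and 8 days (20 − 12).
- A has the same end date as B but full dates, and is correctly not concomitant.
- H shows the limit of the defect. If the known start year precedes the first-dose year, Table 5 gives 1 January of that year and the drug stays non-concomitant.
- E and F have end dates that could overlap treatment, so counting them is reasonable.
- G starts 9 days after last dose. It is concomitant because the first limb has no upper bound; this is a separate matter, taken up under the objection.

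**Adverse events (Table 4, then SAP 10.6.1), applied by hand with the same dates**

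- Start Mar 2022 (day missing), recorded end 12 Mar 2022. The start becomes 20 Mar. The end is recorded, not estimated, so the order check does not act. The event counts as a TEAE that starts 8 days after it ended.
- Start 2022 only, end Feb 2022 (day missing). The end is estimated as 28 Feb and the start becomes 20 Mar. The check now acts and moves the end to 31 Mar. The recorded end month is overwritten, and a pre-dose event becomes a TEAE running from 20 to 31 Mar. Any correction must therefore act before the end-date adjustment.

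**Testing a correction on the medication cases.** Requiring the end to be on or after first dose changes B, C and D to not concomitant. A and H stay not concomitant; E and F stay concomitant. G changes only if a second condition, start no later than last dose, is added.

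**Size.** Frequency cannot be computed, because the documents do not say how many dates are partial. As a scale only: in an arm of the planned 25 subjects, one misclassified subject moves a table entry by at most 1/25 = 4 percentage points. The effect of one subject is larger in the smaller groups left by early stopping and by the split on disease type and AChEI use.

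**The case against.** The strongest reply is that SAP 10.3 already handles pre-dose drugs correctly. That stands for fully dated records: the second limb excludes them, as case A shows. A reader might infer that the SAP counts washed-out drugs as concomitant in general. It does not; a known pre-dose end and a start that is missing or partial in the specific ways listed are both needed. Case H narrows it further.

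A reader might also infer that counting drugs begun after the last dose is an error. The documents do not support that. Concomitant medications are collected at the Week 30 visit, Protocol 8.4 tabulates them with no cut-off at last dose, and the TEAE window in SAP 10.6.1 also extends into follow-up. It is a defensible convention, though unstated, and the second limb's reference to the treatment period leaves the intent unclear.

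A third tempting inference is that a properly stopped prohibited drug would become a deviation and alter the per-protocol set. Nothing links the derived flag to that decision. Prohibited use is settled by discussion among the investigator, Medical Monitor and Sponsor (Protocol 7.3.1), per-protocol exclusions are confirmed before database lock (SAP 7.1.3), and every efficacy parameter in SAP Table 6 uses mITT.

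It is also fair that events are collected only from consent, which limits vague starts; that sites record pre-dose events as pre-treatment; and that listings let a reader find some impossible records. But the SAP does not say that the site's label overrides the imputed date, and a listing does not correct the table.

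**Conclusion.** The defect is real but minor. As written, Tables 4 and 5 can give an item a start later than its recorded end, or presume it treatment-emergent despite that end, and so misclassify medications and adverse events that were over before Day 1. The result is wrong under the SAP's own definitions and, for adverse events, conflicts with Protocol 6.4.1.2.

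The consequence is limited to descriptive safety tables; SAP 10.6.1 plans no between-group comparison of adverse events, and no efficacy analysis is stated to use either classification. The conclusion assumes that the tables are programmed as printed, with no unwritten check on date order. The number of affected records is unknown and may be zero.

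**What to change.** Add one rule to Tables 4 and 5: if a complete or partial end date shows that the item ended before first dose, do not impute the start to the first-dose date. Cap the imputed start at the end date (for a partial end, the latest date it allows) and class the item as prior medication or pre-treatment AE. Apply the rule before any end-date adjustment, and extend it to the Table 4 row that presumes an event with no start date to be treatment-emergent. Items whose end date leaves overlap possible keep the present conservative handling.

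Optionally, add a sentence to SAP 10.3 saying whether medications begun after the last dose count as concomitant or are shown separately. Either choice is acceptable once stated.

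The cost is a few sentences of SAP text and a small programming change, with no new data.
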